1. Title of Project:

Awake caudal catheter infusion versus general anesthesia and single-dose caudal injection for preterm NICU patients undergoing inguinal herniorrhaphy.

2. Principal Investigator: [name], MMS, Nemours Pediatric Surgery

Co-Investigator(s): [name], Nemours Anesthesiology and [name], DO. University of Florida Neonatology

3. Abstract:

This is a prospective, blinded, randomized controlled trial evaluating the effectiveness of awake caudal catheter infusion versus single dose caudal injection and general anesthesia in the surgical management of preterm infant inguinal hernia repair. Currently, the standard of care in the United States is general anesthesia. Spinal anesthesia has been advocated for but highly rejected in the pediatric surgical community due to its high failure rate which can be up to 28%. Spinal anesthesia is a form of regional anesthesia involving injection of a local anesthetic into the subarachnoid space, via a fine needle, in a single injection. The failure rate has to do with the time constraint of spinal anesthesia which is approximately 1 hour. It is difficult to perform a bilateral inguinal hernia in that time duration, necessitating a return trip to the operating room for the contralateral side or intubation midway through the surgical case. We hypothesize that awake caudal catheter infusion will allow for the following benefits (1) greater than 2 hour anesthetic time via redosing which will allow for the completion of the planned surgical procedure (2) exhibit a negligible failure rate (3) minimize post-operative complications that have been associated with general anesthesia in the preterm neonate.

4. Background:

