In the caudal infusion group, Precedex 0.5 mg/kg IV will be administered for sedation over 10 minutes and maintained with an infusion of 0.7 mg/kg/h. Under ultrasound guidance a 20 gauge angio-catheter will be placed into the caudal space and secured to the skin with a tegaderm. A low volume extension catheter will be connected to the angio-catheter and bupivacaine .3% + 1:200,000 epinephrine (dose 3mg/kg) will be administered via the catheter. An additional dose of 1mg/kg will be administered at 1 hour post initial dosing time to extend the duration of the caudal. Intravenous caffeine and rectal Tylenol will be administered for apnea prevention and additional pain control. If patient agitation is noted during the operation, an additional bolus of Precedex 0.5 mg/kg will be administered. If agitation persists, pain, and/or respiratory distress are noted during the operation, general anesthesia will be induced with propofol 3 mg/kg and rocuronium 0.6 mg/kg followed by endotracheal intubation. The angio-catheter will be removed at the end of the surgical procedure. Pain management in the NICU will be the following: mild to moderate pain based on a FLACC scale will receive rectal or oral Tylenol, while moderate-severe pain will receive IV morphine 0.05mg/kg.

Blinding of the study will occur on the day of surgery by the anesthesiologists. Prior to a patient arrival to operating room, the anesthesiologist will randomly draw an envelope from a folder that will allocate group assignment (this precludes bias while discussing patient care with parents and getting consent). It is estimated that we will need approximately 20 patients in each group. 10 envelopes at a time will be placed in the folder, 5 will be in the awake caudal catheter group and 5 will be in the general anesthesia and single-dose caudal group. This will keep the numbers equal when going forward with the study.

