Currently, there are no published articles in the literature to help generate a level of data which can be used to determine the power analysis. We would want a power of 80% and a significance level of 0.05 for the study and after the first 10 patients are enrolled we can calculate a reliable sample size. Based on previous studies conducted in a prospective, randomized fashion we approximate approximately 20 patients in each arm though this is only speculation until the first ten patients are enrolled (Oghazian MB, 2015) (Rakhshani A, 2015) (Mathur NB, 2015). A review from 1/1/2014 – 12/31/14 of NICU patients undergoing inguinal hernia repair at Wolfson was performed and totaled 21. We estimate approximately 80% study inclusion and 20% exclusion. [name], a Nemours statistician will perform all statistical analysis of the study and has indicated the following will be used in the analysis. Demographic and baseline data will be summarized by treatment groups, namely general anesthesia and caudal catheter groups. Quantitative variables will be summarized by mean/SE or median/interquartile range (IQ), whichever appropriate. Categorical variables will be summarized by frequencies and percentages. A chi-square or Fisher exact analysis will be used to compare the general anesthesia group and the caudal catheter infusion group in the primary outcome, which is time to return to baseline respiratory function. A Cox hazard model ratio will compare the hazard risk between the two groups and a log rank test will calculate the median time to return to baseline function. In addition, a Cox proportional hazards model will be used to compare the risk of failure between two groups. A poisson regression analysis will compare the number of bradycardic events, apneic events, catheter complications, and number of post-operative narcotic use days between the general anesthesia group and the caudal catheter infusion group. A logistic regression model will be used to compare the proportion of successful surgical completion between two groups. We estimate the study will run two years for adequate patient accrual. Data will be input by the research nurse and sent for analysis to the statistician for periodic review every three months. Primary outcomes that will be analyzed in the statistical analysis are: time to return of baseline respiratory function, successful surgical completion, catheter complications, number of apneic episodes (defined as cessation of breathing by a premature infant that lasts for more than 20 seconds and/or is accompanied by hypoxia or bradycardia), and bradycardic events (heart rate <90). Secondary outcomes are: days to hospital discharge, number of post-operative narcotic use days, operative time, mechanical ventilation days, and time to full oral feeds.

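### Catheter complications, failure and surgical completion are to be compared between arms, but the control value is fixed or nearly fixed as worded, so the planned ratios are not estimable or usually not

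*Combined protocol and SAP*

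**What the plan says.** All planned models are in the Statistical Analysis part of section 6 of the combined protocol and SAP. Three concern this point:

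- Completion: "A logistic regression model will be used to compare the proportion of successful surgical completion between two groups".
- Failure: "a Cox proportional hazards model will be used to compare the risk of failure between two groups". No event and no time origin are given.
- Catheter complications: "A poisson regression analysis will compare the number of bradycardic events, apneic events, catheter complications", together with narcotic use days.

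The closing list of primary outcomes includes "time to return of baseline respiratory function, successful surgical completion, catheter complications, number of apneic episodes", plus bradycardic events. Earlier, the same section speaks of one primary outcome only: "in the primary outcome, which is time to return to baseline respiratory function".

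Apnea and bradycardia are defined in that list. Completion and failure are not. The nearest guidance is scattered:

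- Aim 1 (section 5) ties a low failure rate to finishing the operation without general anesthesia.
- Section 6 gives the conversion rule for the catheter arm: "If agitation persists, pain, and/or respiratory distress are noted during the operation, general anesthesia will be induced".
- The Abstract expects of the catheter a "greater than 2 hour anesthetic time via redosing which will allow for the completion of the planned surgical procedure", and describes the shortfall of spinal anesthesia as "necessitating a return trip to the operating room for the contralateral side or intubation midway through the surgical case".
- Section 7 says that controls get an injection after intubation and no catheter. It also uses failure in another sense, inadequate pain control.

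**The concern.** A between-arm ratio needs an outcome that can occur, and can fail to occur, in both arms. As worded, catheter complications cannot occur in controls. For completion and failure, the main readings put controls at 0% or near 100% before any infant is enrolled. Logistic, Cox and Poisson ratios have no finite estimate when one arm's cell is empty.

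Aim 1 is one of only two aims, and two of the five listed primary outcomes are affected. Without a definition fixed in advance, the choice of reading can decide whether the trial reports an overwhelming difference or none. A non-significant result on the reading that does address Aim 1 would say little about whether the catheter's failure rate is low.

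**Working it through.** **Inputs.** About 20 infants per arm (section 6; the plan calls this speculative until ten are enrolled). Two-sided 0.05 (the plan gives 0.05; two-sided is an assumption). Catheter failure of 5% (section 4 cites under 5% for caudal anesthesia). Control failure of 1% (an assumption standing for section 5's near-certain completion under general anesthesia; range shown). The 20 per arm cannot be reproduced, because no effect size, rate or SD is given.

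**1. Catheter complications.** With *a* events in the catheter arm and 0 in controls, the rate ratio is (a/20)/(0/20), which is not finite for any *a* > 0 or any sample size. A Poisson fit with one catheter-arm event returns a log rate ratio of 20.4 with a standard error of about 16,206. With six events the Wald p-value is still 0.999.

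**2. Completion without general anesthesia (Aim 1 wording in both arms).** Controls score 0/20 by assignment. For *f* conversions the odds ratio is [(20−f)/f]/(0/20), never finite. A logistic fit of 19/20 v 0/20 gives a log odds ratio of 26.5, standard error about 17,768, p = 0.999.

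**3. Completion under the assigned technique.** The ratio has no finite estimate if either arm has no failures:

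P = 1 − (1 − 0.95^20)(1 − 0.99^20) = 1 − (1 − 0.358)(1 − 0.818) = 0.883.

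| Control failure | P(no finite ratio), catheter 5% |
|---|---|
| 0% | 100% |
| 1% | 88% |
| 2% | 79% |
| 5% | 59% |

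Fisher power, summing the binomial probabilities of all tables with p ≤ 0.05, is 0.2% at 5% v 1% and 3.6% at 10% v 1%.

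**4. Effect of the reading.** Fisher's test is used for illustration; it is not the planned model. Take one conversion in 20:

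- Without general anesthesia: 19/20 v 0/20, p = 2 × C(20,19)/C(40,19) = 40/131,282,408,400 = 3e-10.
- Assigned technique: 1/20 v 0/20 failures, p = 1.0.
- Finished by any means: 20/20 v 20/20, p = 1.0.

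On the first reading, 15 conversions in 20 (5/20 v 0/20 successes) would still give p = 2 × C(20,5)/C(40,5) = 2 × 15,504/658,008 = 0.047 in favor of the catheter.

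**5. What the catheter arm alone can show (Clopper-Pearson 95%).** For 0/20 the upper limit is 1 − 0.025^(1/20) = 16.8%. For 1/20 the interval is 0.1 to 24.9%, and for 2/20 it is 1.2 to 31.7%.

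**The case against.** The plan is not silent. Aim 1 and the conversion rule together imply that failure in the catheter arm means conversion to general anesthesia. That stands: what is missing is a formal analysis definition, above all one that also works for controls.

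Nor is the control value fixed on every conceivable reading, as a reader might infer. Section 7 names inadequate pain control as a failure of either caudal technique, and section 6 says all infants have a caudal procedure. If failure meant inadequate pain control, or catheter complications meant any caudal complication, controls could have events. The Cox sentence follows the return-to-baseline models, so linking its failure to surgical completion is itself an inference. But the plan states none of these meanings, and the reader of the results would have to guess.

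A reader might also infer that the same data could be reported as a significant gain or a significant loss. The figures do not support this for the expected case. A significant loss on the assigned-technique reading needs at least 5 conversions in 20 (p = 0.047; 4 give 0.106). That has a chance of about 0.3% at a true failure rate of 5%, and about 4% at 10%. The realistic choice is between a gain and no difference.

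Finally, 20 per arm is provisional and the 1% is assumed, so the 88% is soft. The results in steps 1 and 2 do not depend on either.

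**Conclusion.** Wrong as written. The catheter-complication rate ratio cannot be estimated at any sample size, taking the term at its word. The completion ratio can never be estimated if Aim 1's wording is applied to both arms, and any difference then reflects assignment. On the assigned-technique reading the ratio usually cannot be estimated at 20 per arm: 88% with 5% v an assumed 1% failure, 100% to 59% for control failure of 0% to 5%.

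The point does not extend to the whole analysis. It gives no ground against the models for return to baseline respiratory function, apnea, bradycardia or narcotic use days.

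**What to change.** Remove catheter complications from the between-arm Poisson list, and drop the logistic and Cox models of completion and failure. Insert, for example:

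*For analysis, failure is the planned operation not completed under the caudal catheter technique: conversion to general anesthesia before the planned operation is finished, or part of the planned repair left undone. Failure, and infants with any catheter complication, are reported among infants randomized to the catheter as n, % and exact (Clopper-Pearson) 95% CI.*

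This defines an endpoint and leaves the clinical conversion rule untouched. If a between-arm contrast is wanted, name one outcome both arms can have, such as any complication of a caudal procedure, and analyze it by a risk difference with an exact interval. Section 5 gives both a failure rate below 96% and one close to 0%; reconcile these before using either as a benchmark.

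**Cost.** No extra infants. The case record must note conversion and any unfinished repair, and the analysis of two listed primary outcomes changes, so this is more than an edit of wording. Aim 1 becomes openly a one-arm and imprecise estimate. At 20 infants, only 0 or 1 failures keep the upper limit below the 28% quoted for spinal anesthesia. The chance of that is 0.95^20 + 20 × 0.05 × 0.95^19 = 74% at a true failure rate of 5%, and 39% at 10%.

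### The plan's own accrual inputs lead one to expect about 34 infants in two years (17 per arm) rather than about 40, and the sample size promised after 10 patients has no stated endpoint, target effect or method

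*Combined protocol and SAP*

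**What the plan says.** All the relevant text is in section 6, Research Plan.

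- **Pool.** Under Statistical Analysis, a review of calendar year 2014 at the site "was performed and totaled 21".
- **Eligibility.** "We estimate approximately 80% study inclusion and 20% exclusion".
- **Duration.** "We estimate the study will run two years for adequate patient accrual".
- **Size.** The paragraph on envelope allocation says "It is estimated that we will need approximately 20 patients in each group". Statistical Analysis repeats the figure with a caveat: "we approximate approximately 20 patients in each arm though this is only speculation until the first ten patients are enrolled".
- **Allocation.** 1:1, by sets of ten envelopes, five for each arm.
- **Route to the final size.** Power of 80% and a 0.05 significance level are wanted, no published data are said to be available for a power analysis, and "after the first 10 patients are enrolled we can calculate a reliable sample size".
- **Refusals.** The consent paragraph expects some parents to decline randomisation. It gives no rate, and no text says whether the 80% already allows for them.

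**The concern.** There are two linked problems.

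First, the pool, inclusion share, duration and size are all given, and multiplying the first three does not return the fourth. Whoever approves or resources the trial would take from it that two years is enough for about 40 infants, which is not what its inputs lead one to expect.

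Second, the plan treats the 20 per arm as a placeholder and relies on a calculation after 10 infants to replace it. That calculation is not defined. Power and significance level alone do not fix a sample size; an endpoint and a target effect are also needed. Statistical Analysis does not settle the endpoint either: one sentence names time to regaining baseline respiratory function as the primary outcome, and a later list gives five primary outcomes. If the gap were filled with an arm difference or a standard deviation (SD) estimated from 10 infants, the resulting number could be far from what 80% power requires.

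**Working it through.** **1. Trying to reproduce the plan's size from its accrual inputs**

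Inputs from Statistical Analysis: 21 repairs a year, 80% included, 2 years. Allocation is 1:1.

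- Expected infants: 21 x 0.80 x 2 = 33.6, or 16.8 per arm (about 34 and 17).
- Stated size: 2 x 20 = 40. Shortfall: 40 - 33.6 = 6.4 infants, or 6.4/40 = 16%.
- Without the 20% exclusion: 21 x 2 = 42, close to 40. In expectation, two years matches the stated size only if the exclusion is left out.
- Expected time to 40: 40 / (21 x 0.80) = 2.38 years = 28.6 months.

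**2. How firm that is**

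The rate rests on one year's count. I treat arrivals as Poisson and the 80% as exact.

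- Exact 95% limits for a count of 21: chi2(0.025, 42)/2 = 13.0 and chi2(0.975, 44)/2 = 32.1 repairs a year. These are limits for the rate, not for future arrivals.
- Chance of 40 or more in two years with 16.8 a year as the true rate: P(Poisson(33.6) >= 40) = 0.154.
- The same chance with uncertainty in the count added (gamma-Poisson prediction, Jeffreys prior, shape 21.5): 0.277.
- 95% prediction ranges under that model: about 18 to 55 infants in two years, and about 17 to 48 months to reach 40.

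**3. Refusals of randomisation**

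The plan gives no rate. If the 80% does not already allow for refusals, two years yields 33.6 x (1 - r) randomised infants. At assumed r of 10%, 20% and 30% this is 30.2, 26.9 and 23.5.

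**4. What the difference in size means**

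The assumptions are a hazard ratio for return to baseline, 1:1 allocation, every infant having the event, and two-sided 0.05 (the plan does not state sidedness). The hazard ratio detectable with 80% power is exp(2 x (1.960 + 0.842) / sqrt(events)).

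- 40 events: 2.43.
- 34 events: 2.61.

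The plan's 20 per arm cannot be checked against a power formula, because no effect, SD or event rate is given.

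**5. What 10 infants can tell**

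Assume 5 per arm.

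- Hazard ratio, all 10 with the event: 95% limits are x/÷ exp(1.96 x sqrt(1/5 + 1/5)) = x/÷ 3.45.
- Pooled SD on 8 degrees of freedom, relevant only to outcomes compared as means: required N scales with the variance. The 95% range for the true variance relative to its estimate is 8/chi2(0.975, 8) = 0.46 to 8/chi2(0.025, 8) = 3.67.

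**The case against.** The strongest reply is that nothing here was offered as firm. The 80%, the two years and the 20 per arm are each labelled an estimate or approximate, the 20 is openly called speculation, and the size is to be revisited after 10 infants. The duration sentence does not mention 40. The prediction range of 18 to 55 infants includes 40, and the practical effect is modest: about 5 more months, or a detectable hazard ratio of 2.61 instead of 2.43.

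Much of this stands, and it rules out several stronger readings.

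- A reader might infer that the duration and the size are incompatible, so that one must be wrong. The documents do not support that: 40 in two years remains possible. What fails is agreement between expected values.
- A reader might infer a failed power calculation. There is none to fail.
- A reader might infer that the observed arm difference in the first 10 infants will set the final size. The plan never says so. The limits in step 5 show why that use, or use of an SD, would be unsafe if the undefined step were filled that way.
- A reader might infer that infants whose parents refuse randomisation will be used to make up the numbers in the between-arm tests. The plan keeps their data and says they will be identified as refusers; no text says they will be pooled.

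The reply does not rescue the plan's description of two years as sufficient, since its own inputs make 40 unlikely in that time. Nor does the intention to revisit the size help while the calculation lacks an endpoint, an effect and a method.

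**Conclusion.** The point holds as an inconsistency in expected values together with an undefined sizing step.

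On the plan's inputs, two years is expected to deliver 33.6 infants, about 17 per arm, against about 40; 40 is expected to take about 29 months. The chance of 40 or more in two years is about 15% to 28%, depending on whether uncertainty in the 2014 count is included. This takes arrivals as Poisson and the 80% as exact. The chance is lower if the 80% does not already cover refusals.

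The accrual gap alone is modest. The missing basis for the final size matters more, because the plan relies on that step in place of a power analysis. Calling its result reliable is unsupported: 10 infants cannot reliably estimate an arm difference (x/÷ 3.45 on a hazard ratio, under the 5-per-arm, all-events assumption) or an SD (N off by 0.46 to 3.67 times, for outcomes compared as means).

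**What to change.** 1. **Make duration and size agree, by one of two routes.** Either state that about 40 infants are expected to need about 29 months, with a 95% prediction range of about 17 to 48 months because the rate comes from a single year's count. Or state that about 34 infants (17 per arm) are expected in two years, with 80% power for a hazard ratio of about 2.61 if every infant has the event. In both cases, say whether the 80% already allows for refusals of randomisation; if it does not, lengthen the duration or reduce the size accordingly.
2. **Define the sizing step.** Delete the word reliable. The sponsor prespecifies the endpoint that drives the size, a clinically justified target effect, and the calculation method. The first 10 infants are used only for arm-combined quantities, such as the share reaching baseline, reported with their limits, and never for the observed arm difference.

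**Cost.** The change is to wording. It brings either a longer stated timeline (28.6 - 24 = about 5 months at the 2014 rate) or a less favourable stated detectable effect (2.61 instead of 2.43). Once the sponsor fixes a target effect, it may call for more infants than either figure.

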 - We hypothesize that awake caudal catheter technique when compared with single-dose caudal injection and general anesthesia will be of greater benefit to preterm infants via the following primary quantifiable measures: reduction in the time to return of baseline respiratory function, reduction in the number of apneic episodes (defined as cessation of breathing by a premature infant that lasts for more than 20 seconds and/or is accompanied by hypoxia or bradycardia), and a reduction in bradycardic events (heart rate <90).
 - We hypothesize that secondary measures will be of greater benefit to preterm infants as well with decreased days to hospital discharge, decreased number of post-operative narcotic use days, decreased mechanical ventilation days, and decreased time to full oral feeds.

Such results are expected to advance the field of pediatric anesthesiology and pediatric surgery which will impact clinical practice by changing the peri-operative management of high risk NICU patients.

6. Research Plan:

Inclusion and Exclusion Criteria

Patients included in the study are preterm infants in the NICU less than 50 weeks post gestational age born at less than 37 weeks gestational age. Patients will be within 1 week of meeting NICU discharge criteria with or without supplemental oxygen prior to surgical scheduling for inguinal hernia repair. Males and females will be included in this study, but there is a known higher incidence of male inguinal hernias in the literature, approximately 6:1.

Patients undergoing other invasive procedures including but not limited to gastrostomy tube placement, tracheostomy, and/or laser eye treatments will be excluded. Any patient with a medical condition that would prevent a regional anesthetic from being performed (i.e. bleeding diathesis, vertebral anomalies, spinal cord injury prior to surgery) and any contradictions to the prescribed medications in the protocol will be excluded.

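### The plan names one primary outcome, then five (three under Aim 2), under a single 0.05 level with no rule for what counts as success

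*Combined protocol and SAP*

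**What the plan says.** Section 6, Statistical Analysis, assigns a between-group test "in the primary outcome, which is time to return to baseline respiratory function". Near its end, the same section states: "Primary outcomes that will be analyzed in the statistical analysis are: time to return of baseline respiratory function, successful surgical completion, catheter complications", and adds apneic episodes and bradycardic events, which makes five.

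Section 5, Aim 2, gives a third version. Benefit is to be shown "via the following primary quantifiable measures: reduction in the time to return of baseline respiratory function", together with fewer apneic episodes "and a reduction in bradycardic events (heart rate <90"). That makes three.

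On error and power, the Statistical Analysis section says: "We would want a power of 80% and a significance level of 0.05 for the study". On size: "we approximate approximately 20 patients in each arm though this is only speculation until the first ten patients are enrolled". It gives no effect size, event rate, standard deviation or hazard ratio.

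The outcomes are analysed separately. Recovery time has chi-square or Fisher, Cox and log-rank methods. Apnea, bradycardia and catheter complications have Poisson regression. For completion: "A logistic regression model will be used to compare the proportion of successful surgical completion between two groups". Neither section says how many of these comparisons must succeed, in what order they are tested, how the 0.05 is shared, or whether tests are one- or two-sided.

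**The concern.** With one, three and five primary outcomes all in the text, a reader cannot tell what result would support the study's claim. Each outcome has its own comparison, so nothing stops a win on any one of them from being reported as a primary success. On that reading the stated 0.05 does not hold for the study as a whole. On the opposite reading, that every Aim 2 measure must succeed, the error rate is safe but the stated 80% power is not reached.

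The sample size is affected too. The plan promises to calculate it after ten patients, but a time to event, an event count and a proportion need different inputs and give different answers. Until one outcome is chosen, that calculation is undefined.

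**Working it through.** **The plan's own figure.** About 20 per arm cannot be reproduced, because no effect size is given for any outcome.

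**Inputs.** Level 0.05, power 80% and about 20 per arm come from Statistical Analysis. Sidedness is not stated; two-sided is assumed, which puts 0.025 in the benefit direction for each outcome. Correlation between test statistics is not given; 0 to 0.7 is assumed. Some positive correlation is likely, because an apneic episode is one that "lasts for more than 20 seconds and/or is accompanied by hypoxia or bradycardia".

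**1. Which outcomes can produce a false benefit.** Section 5 says general anesthesia allows completion practically always, so the catheter arm has little room to win on completion. Section 7 says control infants receive no catheter. That leaves recovery, apnea and bradycardia, which are the three Aim 2 measures.

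**2. If any one win counts** (assumption; each test holds its level):
- One outcome: 2.5%.
- Three, independent: 1 − 0.975³ = 7.3%.
- Three, equal correlation ρ: 1 − ∫ φ(u) Φ((1.96 − √ρ·u)/√(1 − ρ))³ du = 6.8%, 6.3% and 5.5% at ρ = 0.3, 0.5 and 0.7.
- Five taken literally: 1 − 0.975⁵ = 11.9% if independent, and 7.4% at ρ = 0.7.
- Three outcomes with one-sided 0.05 tests: 1 − 0.95³ = 14.3% if independent, and 10.3% at ρ = 0.7, against 5% for one outcome.

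**3. The three-outcome range is not a ceiling.** Take the planned logistic regression on completion with 20 per arm and a likelihood-ratio test. The chance of a false benefit is 0.08% at an assumed 1% failure in both arms and 2.7% at an assumed 5%. At 5%, adding completion as independent gives 1 − (1 − 0.0731)(1 − 0.0272) = 9.8%.

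**4. If all three Aim 2 measures must succeed.** False benefit is at most 2.5%. With 80% power for each, joint power is 0.8³ = 51% if independent, 61% at ρ = 0.5 and 66% at ρ = 0.7.

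**5. What the size supports if recovery time is the outcome.** Log-rank events for 80% power at two-sided 0.05 are 4(1.960 + 0.842)²/(ln HR)².
- HR 1.5, 2.0 and 2.5 (assumed) give 191.0, 65.3 and 37.4 events.
- If all 40 infants reach baseline, the detectable HR is exp(2 × 2.802/√40) = 2.43.
- Accrual from the Statistical Analysis section: 21 cases a year × 0.80 included × 2 years = 33.6, about 34 infants. With 34 events the detectable HR is exp(2 × 2.802/√34) = 2.61.

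**The case against.** The strongest reply is that the harm is conditional. No section says that one win is enough. Aim 2 joins its three measures with a conjunction, so requiring all three is a possible reading, and on it nothing is inflated. This stands: what is documented is ambiguity, not a demonstrated error rate. It does not rescue the plan, because the all-three reading misses the stated 80% power, and no section adopts it.

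A second reply is that the plan does name one primary outcome. It does, but the list of five comes later in the same section and is just as explicit.

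A third concerns the restriction to three outcomes. Catheter complications are not defined, and section 7 discusses adverse events of catheter and single-shot placement together. If the outcome were scored as any caudal complication, both arms could have events and it could favour either arm. The restriction is reasonable, not certain.

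A fourth concerns the remedy. Section 6, in describing the general anesthesia arm, says the study asks whether exposure to general anesthesia alters how likely apnea and bradycardia are. Simply demoting those two outcomes would set aside a question the investigators put at the centre. This stands, and the fix allows for it.

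A reader might also infer that, with five outcomes listed, the false-benefit risk is 11.9%. That needs all five to be independent and equally able to favour the catheter arm, which sections 5 and 7 make unlikely.

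**Conclusion.** The point holds as an unresolved definition of success. One, three and five primary outcomes stand side by side under one 0.05 level with no rule linking them, and the sample size is tied to none.

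The size depends on the reading. If any one win counts, with two-sided 0.05 tests that hold their level, false benefit across the three Aim 2 outcomes is 5.5% to 7.3% at correlation 0.7 to 0, against 2.5% for one outcome. All five taken literally give 7.4% to 11.9%. With completion at 5% failure in both arms and independence, the three-outcome figure rises to about 9.8%. If all three must succeed, there is no inflation, and joint power is 51% to 66%.

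A reader might go further and conclude that the trial will exceed its error rate. The documents do not support that, because they state no success rule, sidedness or correlation. Nor do they compel the view that apnea and bradycardia must lose confirmatory status; that choice belongs to the sponsor.

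**What to change.** State one success rule, in the same terms, in Aim 2 and in Statistical Analysis:

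- Keep recovery time as the primary outcome, as Statistical Analysis already says. Test it once at two-sided 0.05 by log-rank, with the Cox hazard ratio and 95% CI as the estimate, in place of the chi-square/Fisher assignment.
- Test apnea and then bradycardia in a fixed order, each at two-sided 0.05 and only if the test before it succeeds. Alternatively, the sponsor may name both secondary.
- Report Aim 1 completion as the catheter-arm failure rate with an exact 95% CI, and catheter complications descriptively. Neither should carry a between-arm primary claim.
- Base the sample size on recovery time, with a hazard ratio fixed in advance.

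**Cost.** Data collection does not change. The fixed order costs recovery time no power; by contrast, a Holm procedure over three outcomes would cut 80% to about 66% at its first step, Φ(2.802 − 2.394). The price of the order is that apnea and bradycardia can be claimed only if the earlier tests succeed. The Aim 1 interval is wide: 0 failures in 20 gives 0 to 1 − 0.025^(1/20) = 16.8%.

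The larger consequence is that naming the endpoint may show the study can detect only large effects: a hazard ratio of about 2.4 with 40 events, or 2.6 with the 34 infants that the stated accrual gives in two years. The detectable effect should be restated accordingly.
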